8.5. Statistical Significance Level

All planned analysis will be conducted with an overall type I error rate of 5%. There will be neither adjustment for multiple tests nor adjustment for multiplicity of endpoints. Unless otherwise specified, all statistical tests will be 2-sided.

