14.4. Level of Statistical Significance

The primary and secondary hypotheses will be tested with a type I error of 5% individually.

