5.3. Other Hypotheses

1. The Test lens will be superior to the Control lens in all 9 of the following lens preference items at the two-week follow-up evaluation of the second wearing period.
 - a) Overall lens preference
 - b) Overall comfort
 - c) Overall vision
 - d) Overall reduction of glare
 - e) Overall preference indoors
 - f) Overall preference outdoors
 - g) Overall preference while driving during the day
 - h) Overall preference while driving at night
 - i) Overall preference while using computer screens & digital devices
2. The Test lens will be superior to the Control lens in at least 2 of the following 4 indoor performance measures at the two-week follow-up evaluation.
 - a) Reduction in squinting while using computer screens or digital devices

- b) Reduction in glare from the computer screen or digital devices
- c) Reduction in glare caused by bright indoor lights
- d) Reduction in glare caused by bright light coming through the window

3. The Test lens will be non-inferior to the Control lens with respect to both of the following driving performance metrics at the two-week follow-up evaluation. A cumulative odds ratio margin of 0.67 will be used.

- a) Reduction in glare while driving during the day
- b) Reduction in glare while driving during the night

4. The Test lens will be superior to the Control lens in at least 2 of the following 4 outdoor performance measures at the two-week follow-up evaluation.

- a) Ability to see comfortably in bright sunlight
- b) Reduction in glare in bright sunlight
- c) Reduction in squinting in bright sunlight
- d) Reduction in eye strain in bright sunlight

5. At the 2-week follow-up evaluation, the difference in the area under the contrast sensitivity function curve (measured by the quick Contrast Sensitivity Function (qCSF) method) between the Test lens and the Control lens is more than -0.3 log unit.

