Non-inferiority will be declared if the lower bound of the 2-sided 95% credible interval of the difference between the Test lens and the Control lens is greater than -5, i.e., $P(\beta_1 > -5) \geq 0.975$.

Vision Satisfaction in Bright Lighting

Vision satisfaction in bright lighting will be analyzed using a Bayesian multinomial model for ordinal data. The regression model will include sequence of lens wear, lens type, period and first order carryover effect. Clinical site and subject nested within clinical site will be included as random effects. Other subject characteristics such as age, gender, race and iris category will be included when appropriate.

The Model:

Let $y_{ijklm} = (y_{ijklm1}, y_{ijklm2}, y_{ijklm3}, y_{ijklm4}, y_{ijklm5})$ denote the rating for the m^{th} subject, from the l^{th} site, assigned to the i^{th} study lens in the j^{th} period using the k^{th} sequence. Possible values of y_{ijklm} are 1 if the subject rating of vision satisfaction in bright lighting are X and 0 otherwise (x=1 for Strongly Agree and X=5 for Strongly Disagree, respectively). The likelihood is constructed as follows:

$$y_{ijklm} \sim \text{Multinomial}(P_{ijklm1}, P_{ijklm2}, P_{ijklm3}, P_{ijklm4}, P_{ijklm5})$$

$$P_{ijklm1} = \gamma_{ijklm1}$$

$$P_{ijklmX} = \gamma_{ijklmX} - \gamma_{ijklm(X-1)} \quad 2 \leq n \leq 4$$

$$P_{ijklm5} = 1 - \sum_{x=1..4} P_{ijklmX}$$

$$\text{Logit}(\gamma_{ijklmX}) = \theta_n + \beta_1 \text{Lens}_{i[j,k]} + \beta_2 \text{Period}_{j1} + \beta_3 \text{Period}_{j2} + \beta_4 \text{Sequence}_k + \beta_5 \text{Carry}_{i[j,k]} + \gamma_l + \delta_{m(l)}$$

Where θ_n is the intercept for levels n=1,2,3,4, $P_{ijklm1} = \text{Pr}(\gamma_{ijklm1} = 1)$ with respect to the vision satisfaction in bright lighting item. We assume the random subject effects are independent identically distributed (i.i.d) as $\delta_{m(l)} \sim N(0, \sigma_{\text{subject}}^2)$ for subject m nested within clinical site l and

the random clinical site effects are i.i.d as $\gamma_l \sim N(0, \sigma_{site}^2)$ for $i=1,2$ (lens), $j=1, 2, 3$ (Period) $k=1, 2$ (Sequence) $l=1, \dots, 6$ (Site) $m=1, \dots, n_l$ (subject/site).

In this model, the lens I will be determined by the period j and sequence k , therefore i is denoted as a function of j and k . We define $Lens_i=0$ for the Control lens and $Lens_i=1$ for the Test lens. The cumulative odds ratio for having higher rating can be written as $OR=e^{\beta_1}$.

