11.2. Secondary Analysis

Secondary efficacy analysis:

CLUE Overall Quality of Vision and Handling

CLUE Overall Quality of Vision and Handling will be analyzed and test in the exact same manner as CLUE Overall Comfort.

Overall Quality of Vision Indoors

Overall quality of vision indoors will be analyzed and tested in the same manner as vision satisfaction in bright lighting. The only difference between the two models are the response set used to assess each item. For this model,

Let $y_{ijklm} = (y_{ijklm1}, y_{ijklm2}, y_{ijklm3}, y_{ijklm4}, y_{ijklm5})$ denote the rating for the m^{th} subject, from the l^{th} site, assigned to the i^{th} study lens in the j^{th} period using the k^{th} sequence. Possible values of y_{ijklm} are 1 if the subject rating of overall quality of vision indoors are X and 0 otherwise (x=1 for Excellent and X=5 for Poor, respectively).

Secondary safety analysis:

Not Applicable

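### SAP 8.5 claims a 5% overall type I error with no multiplicity adjustment; the decision rules deliver this for the primaries, but not for three secondaries claimed separately

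*SAP*

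**What the plan says.** **Error rate.** SAP 8.5 states: "All planned analysis will be conducted with an overall type I error rate of 5%. There will be neither adjustment for multiple tests". The same sentence goes on to exclude any correction for having several endpoints. The default for sidedness is also set there: "Unless otherwise specified, all statistical tests will be 2-sided". Protocol 14.4 reads differently: "The primary and secondary hypotheses will be tested with a type I error of 5% individually". SAP section 1 and Protocol 14.3 give the SAP precedence over the protocol's statistical section, so the SAP wording governs.

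**Decision rules.** For non-inferiority on CLUE comfort, SAP 11.1 sets this condition: "lower bound of the 2-sided 95% credible interval of the difference between the Test lens and the Control lens is greater than -5". That is a posterior probability of at least 0.975. SAP 11.2 carries this over: "CLUE Overall Quality of Vision and Handling will be analyzed and test in the exact same manner as CLUE Overall Comfort". The third secondary, quality of vision indoors, follows the bright-lighting item: the lower 95% limit of the cumulative odds ratio must lie above 0.67, again at 0.975.

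**Success rules.** SAP 5.1 ties the primary objective to meeting all the primaries. SAP 5.2 lists three secondary hypotheses with no joint rule, no order and no dependence on the primaries. Protocol 2.3 goes further than SAP 5.1: the study objective is satisfied only if every primary and every secondary hypothesis is met.

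**Exploratory rules.** SAP 5.3 states: "The Test lens will be superior to the Control lens in at least 2 of the following 4 outdoor performance measures". It has a matching rule for the indoor items. SAP 11.3 tests each item at 0.975. SAP section 2 and Protocol 2.1 present these items as exploratory, and Protocol 14.7 plans only descriptive summaries, with further analysis optional.

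**The concern.** An overall rate of 5% is a statement about a family of tests. Running each test at the conventional level without adjustment gives that rate only if some other rule ties the tests together. The SAP has such a rule for the primaries and none for the secondaries. The protocol's accurate per-hypothesis statement is therefore displaced, in the governing document, by one that the decision rules do not support.

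At stake is how the secondary results may be described. A report that follows SAP 8.5 could credit separate secondary claims with a 5% overall error rate that they do not have. These endpoints are not peripheral: SAP 8.4 says vision indoors was the main driver of the sample size.

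**Working it through.** **Inputs.** Per-test threshold 0.975 (SAP 11.1 to 11.3); three secondaries (SAP 5.2); two of four items for the indoor and for the outdoor rule (SAP 5.3). Assumption: with the vague priors specified, a posterior probability of 0.975 has a frequentist error of about 0.025 in the tested direction. The documents give no correlation between endpoints, so a range is shown.

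**1. The plan's own figure.** One test: 1 − 0.975 = 0.025 in the tested direction, or 2 × 0.025 = 0.05 two-sided. The stated 5% is reproduced for a single test, as in Protocol 14.4.

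**2. Primaries.** All must be met, so a false overall primary claim requires an error on at least one hypothesis that is truly not met. Its probability is at most 0.025. The stated level holds without adjustment.

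**3. Secondaries claimed one by one, none truly non-inferior.** Under independence, P(at least one false claim) = 1 − 0.975³ = 0.0731. The bound under any dependence is 3 × 0.025 = 0.075. For equally correlated normal statistics with correlation ρ, P = 1 − ∫ φ(u) Φ[(1.96 − √ρ·u)/√(1 − ρ)]³ du:

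| ρ | P(at least one false secondary claim) |
|---|---|
| 0 | 7.3% |
| 0.3 | 6.8% |
| 0.5 | 6.3% |
| 0.7 | 5.5% |
| 0.8 | 4.9% |
| 0.9 | 4.2% |

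The curve crosses 5% at ρ of about 0.79.

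**4. Secondaries under Protocol 2.3.** If all must be met, the argument of step 2 applies and the error is at most 2.5% in the tested direction.

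**5. Two of four, no item truly superior.** Under independence: 1 − 0.975⁴ − 4 × 0.025 × 0.975³ = 0.0036. At correlation 0.5 it is 1.7%, and at 0.9 it is 2.7%. By Markov's inequality it cannot exceed 4 × 0.025 / 2 = 0.05 under any dependence.

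**6. Two of four, exactly one item truly superior.** The claim is then false if a second item passes in error. If the superior item is certain to be detected and the other three are independent: 1 − 0.975³ = 0.0731. If it is detected with 80% power: 0.8 × 0.0731 + 0.2 × P(at least two of three in error) = 0.8 × 0.0731 + 0.2 × 0.0018 = 0.0589.

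**The case against.** The strongest reply is Protocol 2.3. It makes the secondaries part of an all-must-be-met rule, which needs no adjustment. It lies outside the statistical section that the SAP supersedes, and SAP 5.1 does not expressly withdraw it. SAP section 2 also words the secondary objective as one joint aim. This stands to the extent that, if Protocol 2.3 governs, the study-level conclusion is controlled. It does not settle the matter: SAP 5.1 limits its rule to the primaries, SAP 5.2 has none, and nothing bars a single secondary from being claimed on its own.

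It is also fair to say that SAP 8.5 openly disclaims adjustment, that the excess over 5% is at most 7.5 − 5 = 2.5 percentage points, and that it disappears under high correlation. The three secondaries are ratings by the same wearers, two of them of vision quality, so sizeable correlation is plausible.

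Four stronger readings are tempting but not supported:

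- *The primary conclusion is at risk.* It is not; see step 2.
- *The two-of-four rules inflate the error in general.* They are conservative when no item is superior. The excess needs exactly one truly superior item, on endpoints that both documents call exploratory.
- *The rate for the three secondaries is 1 − 0.95³ = 14.3%.* That takes 5% as the directional rate, but every rule uses 0.975.
- *A study-wide rate follows from multiplying up all the non-primary claims.* The preference rule needs all nine items and the driving rule needs both, so they do not behave like single tests. SAP 11.3 gives no decision rule for contrast sensitivity, and the correlations are unknown.

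**Conclusion.** The concern holds in limited form. The overall claim in SAP 8.5 conflicts with Protocol 14.4 and is not what the decision rules deliver. For the secondaries, the chance of at least one false claim is about 7.3% under independence and 5.5% at correlation 0.7. It is below 5% only above about 0.79, and it applies only if they are claimed separately. SAP 5.1 and 5.2 leave that open, while Protocol 2.3 would close it; this is a second inconsistency to resolve with the first. For the two-of-four rules the excess is conditional: up to about 7.3% with one item truly superior and certain to be detected, or 5.9% at 80% power for it, both with the other items independent.

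These figures rest on vague priors giving about 2.5% per directional test and, where correlation enters, on equally correlated normal statistics. The primary analysis is unaffected.

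**What to change.** 1. In SAP 8.5, replace the *overall* statement with 5% per hypothesis (2.5% in the tested direction), and say that the primaries are controlled because all must be met.
2. Reconcile Protocol 2.3 with SAP 5.1 and 5.2. Either require all three secondaries to be met for any secondary claim, or test them in a prespecified fixed order only after all primaries are met. Both keep the secondary error at or below 2.5% in the tested direction without splitting alpha.
3. Label the two-of-four results and the other exploratory results as not controlled for multiplicity. A stricter per-item threshold is optional and not needed to correct the defect.

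**Cost.** SAP wording, with a matching clarification of Protocol 2.3 if a fixed order is chosen. The primaries lose no power. Under a fixed order, later secondaries lose some; under all-must-be-met, one failure blocks every secondary claim. The order needs thought because vision indoors drove the sample size. SAP Table 12 gives it 81% power with 95 completers, against 81% and 82% with 30 completers for the two CLUE secondaries, and 105 completers are planned. Placed first, a miss on vision indoors would block both CLUE claims; placed last, it depends on two hypotheses that the plan regards as far easier to meet.

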8.6. Handling of Missing Data and Drop-outs

Missing or spurious values will not be imputed. The count of missing values will be included in the summary tables and listings.

Subject dropout is expected to be one of the main reasons of missing data in this clinical trial. Past clinical trials don't provide the evidence that subject dropout is systematic or not-atrandom. To evaluate the impact of missing data, sensitivity analysis will be conducted using multiple imputation methods if the proportion of subject dropout is greater than the 15%. The SAS/STAT procedures PROC MI and PROC MIANALYZE will be utilized with a parametric regression method used to make at least 10 imputations.

9. INTERIM ANALYSIS AND DATA MONITORING COMMITTEE REVIEW

An interim analysis will be conducted after the first 75 subjects complete the first wearing period or 4-weeks post first subject first visit. The interim analysis will consist of descriptively summarizing safety and efficacy parameters. The results will be reviewed with historical data with lenses from the pilot line before the design validation study, [REDACTED] is initiated. The results will be communicated to study responsible clinician, project lead and platform lead. No statistical analysis will be conducted on the interim data.

10. SUBJECT INFORMATION

10.1. Disposition Information

Enrolled subjects will be allocated to one of the three mutually exclusive:

1. Completed: Subjects are considered to have completed the study if they (a) provided informed consent and/or assent; (b) they are eligible; (c) completed all three phases of testing; and (d) have not withdrawn/discontinued from the study.
2. Discontinued: Subjects are considered to have discontinued from the study if (i) test article was administered and (ii) discontinued from the study. Reasons for discontinuation include: (a) subject's death during the study period (b) subject withdrawal of consent and/or assent (c) subject not compliant to protocol (d) subject lost to follow-up (e) subject no longer meets eligibility criteria (e) subject develops significant or serious adverse events causing discontinuation of study lens wear (f) subject who have experience a Corneal Infiltrative Event (g) investigator's clinical judgement regarding the subject safety reasons (that it is in the best interest of the subject to stop treatment) (h) subject missed any scheduled visit.
3. Assigned and Test Article Administered: Total number subjects for which test articles were administered (Completed + Discontinued).

4. Enrolled but Not Dispensed: Subjects are considered to be Enrolled Not Dispensed Subjects if they were (i) enrolled to the study (provided informed consent and/or assent) but failed to satisfy the eligibility criteria (inclusion/exclusion criteria) or (ii) if they are randomized but did not receive a test article.
5. Total enrolled: Completed + Discontinued + Enrolled but Not Dispensed.

10.2. Protocol Deviations

Any protocol deviation that could impact the primary endpoints will result in the subject being excluded from the Per-Protocol analysis population. No analysis on protocol deviations will be performed. All reported protocol deviations will be listed.

10.3. Demographics and Baseline Characteristics

Demographic characteristics will be summarized by Per-Protocol, safety, all enrolled and by lens sequence population using descriptive statistics for continuous variables, and numbers and percentages of subjects for categorical variables. Demographic information will include age, gender, race and ethnicity and iris category.

10.4. Treatment Compliance and Extent of Exposure

Average daily wear time and average daily comfort wear time will be provided in the summary table. Non-compliance will be reported in protocol deviation.

10.5. Prior and Concomitant Medications

Prior and concomitant medications will be documented during screening and updated during the study when applicable. A listing for both prior and concomitant medications will be created for all enrolled subjects.

Disallowed medications for this study include: Oral retinoid isotretinoin (e.g. Accutane), oral tetracyclines, topical scopolamine, oral (e.g. Seldane, Chlor-Trimeton and Benadryl) and ophthalmic antihistamines, oral phenothiazines (e.g. Haldol, Mellaril, Thorazine, Elavil, Pamelor and Compazine), oral and ophthalmic Beta-Adrenergic blockers (e.g. Propranolol, Timolol and Practolol), systemic steroids and any prescribed or over the counter (OTC) ocular medication.

There are no disallowed concomitant therapies in this study.

10.6. Medical History

A listing of medical and surgical history will be created for all enrolled subjects.

11. STATISTICAL ANALYSIS

11.1. Primary Analysis

Primary efficacy analysis:

CR-6283, Statistical Analysis Plan Version 2.0

Page 21 of 32

Visual Acuity

Distance monocular visual acuity (logMAR) will be tested under two conditions (bright illumination low contrast and dim illumination high contrast). Each condition will be analyzed separately using a Bayesian multivariate normal random-effects model to compare the Test and Control lenses. The regression model will include sequence of lens wear, lens type and first-order carryover effect as fixed effects. Clinical site and subject nested within clinical site will be included as random effects. Other subject characteristics such as gender and age will be included as fixed effects when appropriate.

The Model:

Let $y_{ijklm} = (y1_{ijklm}, y2_{ijklm}, y3_{ijklm})$ denote the visual acuity (logMAR) for the m^{th} subject at the l^{th} site, assigned to the i^{th} lens for the j^{th} eye using the k^{th} sequence at periods 1, 2, 3, respectively. The likelihood for y_{ijklm} is constructed as follows:

$$y_{ijklm} \sim N(\mu_{ijklm}, \Sigma)$$

Where $\mu_{ijklm} = (\mu1_{ijklm}, \mu2_{ijklm}, \mu3_{ijklm})^T$ and Σ is a 3X3 variance-covariance matrix. Here,

$$\begin{aligned}\mu1_{ijklm} &= \mu_0 + \pi_1 + \beta_1 \text{Lens}_{[i,k]} + \beta_2 \text{Sequence}_k + \gamma_l + \alpha_j \\ \mu2_{ijklm} &= \mu_0 + \pi_2 + \beta_1 \text{Lens}_{[i,k]} + \beta_2 \text{Sequence}_k + \beta_3 \text{Carry1}_{[i,k]} + \gamma_l + \alpha_j \\ \mu3_{ijklm} &= \mu_0 + \pi_3 + \beta_1 \text{Lens}_{[i,k]} + \beta_2 \text{Sequence}_k - \beta_3 \text{Carry1}_{[i,k]} + \gamma_l + \alpha_j\end{aligned}$$

In this model π_1, π_2, π_3 represent the effect of period with the constraint $\pi_1 + \pi_2 + \pi_3 = 0$. Lens will be determined by sequence k therefore lens i is denoted as a function of k. We define $\text{Lens}_i=0$ for the Control lens and $\text{Lens}_i=1$ for the Test lens, sequence is defined as: Sequence=0 for the order Control/Test/Test and Sequence=1 for order Test/Control/Control. The first-order carryover effect will be defined as carry=0 for the Control lens and carry=1 for the Test lens. So β_1 stands for the difference between the Test and Control lens with respect to visual performance. A negative β_1 indicates the Test performed better than the Control lens.

We assume random subject eye effects are independent and identically distributed (i.i.d) as $\alpha_j \sim N(0, \sigma_{eye}^2)$ and the random subject effect is i.i.d. as $\delta_m \sim N(0, \sigma_{subject}^2)$ and the random site effect is i.i.d as $\gamma_l \sim N(0, \sigma_{site}^2)$ for $i=1,2$ (lens), $j=1, 2$ (eye), $k=1, 2$ (sequence), carry1=1, 2 (first-order carryover effect) and $l=1\dots|m_l(\text{subject/site})$ and $l=1, 2, 3, 4, 5$ and 6 (site).

For the β coefficients, independent non-informative priors $N(0, 1000)$ will be used. For the variance of random effects σ_{eye}^2 and σ_{site}^2 independent non-informative conjugate priors inverse-gamma(0.001, 0.001) will be used. For Σ , non-informative conjugate priors inverse-wishart(3,S) will be used where S is a 3X3 variance-covariance matrix of y_{ijklm} . The metropolis sampler algorithm as implemented in the SAS/STAT MCMC 14.2¹⁴ procedure will be used to estimate the posterior distribution of the unknown parameters. Inferences will be made based on the 95% posterior credible intervals for relevant parameters.

Hypothesis Testing

The null and alternative hypothesis for visual acuity (logMAR) to test for non-inferiority of the Test lens relative to the Control lens is as follows:

$$\begin{aligned} H_0: \beta_1 &\geq 0.05 \\ H_A: \beta_1 &< 0.05 \end{aligned}$$

Non-inferiority will be declared if the upper limit of the 95% credible interval of the difference between the Test and Control is below 0.05, i.e. $P(\beta_1 < 0.05) \geq 0.975$.

CLUE Overall Comfort

CLUE Comfort scores will be analyzed using a Bayesian multivariate normal random-effects model to compare the Test and Control lenses. The regression model will include baseline CLUE comfort scores, sequence of lens wear, lens type and first-order carryover effect as fixed effects. Clinical site will be included as random effects. Other subject characteristics such as age, gender, race and iris category will be included when appropriate.

The Model:

Let $y_{ijkl} = (y1_{ijkl}, y2_{ijkl}, y3_{ijkl})$ denote the CLUE Comfort score for the l^{th} subject at the k^{th} site, assigned to the i^{th} lens using the j^{th} sequence at periods 1, 2 and 3. The likelihood for y_{ijkl} is constructed as follows:

$$y_{ijkl} \sim N(\mu_{ijkl}, \Sigma)$$

Where $\mu_{ijkl} = (\mu1_{ijkl}, \mu2_{ijkl}, \mu3_{ijkl})^T$ and Σ is a 3X3 variance-covariance matrix. Here,

$$\begin{aligned} \mu1_{ijkl} &= \mu_0 + \pi_1 + \beta_1 \text{Lens}_{[i,j]} + \beta_2 \text{baseline} + \beta_3 \text{Sequence}_j + \gamma_k \\ \mu2_{ijkl} &= \mu_0 + \pi_2 + \beta_1 \text{Lens}_{[i,j]} + \beta_2 \text{baseline} + \beta_3 \text{Sequence}_j + \beta_4 \text{Carry1}_{[i,j]} + \gamma_k \\ \mu3_{ijkl} &= \mu_0 + \pi_3 + \beta_1 \text{Lens}_{[i,j]} + \beta_2 \text{baseline} + \beta_3 \text{Sequence}_j - \beta_4 \text{Carry1}_{[i,j]} + \gamma_k \end{aligned}$$

In this model π_1, π_2, π_3 represent the effect of period with the constraint $\pi_1 + \pi_2 + \pi_3 = 0$. Lens will be determined by sequence j, therefore i is denoted as a function of j. We define Lens=0 for the Control lens and Lens = 1 for the Test lens, sequence is defined as: Sequence=0 for the order Control/Test/Test and Sequence=1 for order Test/Control/Control. The first-order carryover effect will be defined as carry=0 for the Control lens and carry=1 for the Test lens. So β_1 stands for the difference between the Test and Control lens with respect to CLUE comfort; A positive β_1 indicates the Test performed better than the Control.

We assume random site effects are independent and identically distributed (i.i.d) as $\gamma_k \sim N(0, \sigma_{site}^2)$ for site for $i=1, 2$ (lens), $j=1, 2$ (sequence), $k=1, 2, 3, 4, 5$ and 6 (site).

For the β coefficients, independent non-informative priors $N(0, 1000)$ will be used. For the variance of random effect of σ_{site}^2 an independent non-informative conjugate prior, inverse-gamma(0.001, 0.001) will be used. For Σ , non-informative conjugate priors inverse-wishart(3,S) will be used where S is a 3X3 variance-covariance matrix of y_{ijkl} . Starting values for the mean and variance of CLUE scores will be 60 and 400 (since standard deviation of CLUE is normalized to be 20), respectively. The Metropolis sampler algorithm as implemented in the SAS/STAT MCMC 14.2¹⁴ procedure will be used to estimate the posterior distribution of the unknown

parameters. Inferences will be made based on the 95% posterior credible intervals for relevant parameters.

Hypothesis Testing

The null and alternative hypotheses for CLUE comfort non-inferiority of the Test lens relative to the Control lens are as follows:

$$H_0: \beta_1 \leq -5$$

$$H_A: \beta_1 > -5$$

Non-inferiority will be declared if the lower bound of the 2-sided 95% credible interval of the difference between the Test lens and the Control lens is greater than -5, i.e., $P(\beta_1 > -5) \geq 0.975$.

Vision Satisfaction in Bright Lighting

Vision satisfaction in bright lighting will be analyzed using a Bayesian multinomial model for ordinal data. The regression model will include sequence of lens wear, lens type, period and first order carryover effect. Clinical site and subject nested within clinical site will be included as random effects. Other subject characteristics such as age, gender, race and iris category will be included when appropriate.

The Model:

Let $y_{ijklm} = (y_{ijklm1}, y_{ijklm2}, y_{ijklm3}, y_{ijklm4}, y_{ijklm5})$ denote the rating for the m^{th} subject, from the l^{th} site, assigned to the i^{th} study lens in the j^{th} period using the k^{th} sequence. Possible values of y_{ijklm} are 1 if the subject rating of vision satisfaction in bright lighting are X and 0 otherwise (x=1 for Strongly Agree and X=5 for Strongly Disagree, respectively). The likelihood is constructed as follows:

$$y_{ijklm} \sim \text{Multinomial}(P_{ijklm1}, P_{ijklm2}, P_{ijklm3}, P_{ijklm4}, P_{ijklm5})$$

$$P_{ijklm1} = \gamma_{ijklm1}$$

$$P_{ijklmX} = \gamma_{ijklmX} - \gamma_{ijklm(X-1)} \quad 2 \leq n \leq 4$$

$$P_{ijklm5} = 1 - \sum_{x=1..4} P_{ijklmX}$$

$$\text{Logit}(\gamma_{ijklmX}) = \theta_n + \beta_1 \text{Lens}_{i[j,k]} + \beta_2 \text{Period}_{j1} + \beta_3 \text{Period}_{j2} + \beta_4 \text{Sequence}_k + \beta_5 \text{Carry}_{i[j,k]} + \gamma_l + \delta_{m(l)}$$

Where θ_n is the intercept for levels n=1,2,3,4, $P_{ijklm1} = \text{Pr}(\gamma_{ijklm1} = 1)$ with respect to the vision satisfaction in bright lighting item. We assume the random subject effects are independent identically distributed (i.i.d) as $\delta_{m(l)} \sim N(0, \sigma_{\text{subject}}^2)$ for subject m nested within clinical site l and

the random clinical site effects are i.i.d as $\gamma_l \sim N(0, \sigma_{site}^2)$ for $i=1,2$ (lens), $j=1, 2, 3$ (Period) $k=1, 2$ (Sequence) $l=1, \dots, 6$ (Site) $m=1, \dots, n_l$ (subject/site).

In this model, the lens I will be determined by the period j and sequence k , therefore i is denoted as a function of j and k . We define $Lens_i=0$ for the Control lens and $Lens_i=1$ for the Test lens. The cumulative odds ratio for having higher rating can be written as $OR=e^{\beta_1}$.

Independent vague $N(0, 1000)$ priors for the regression coefficients β_i $i=1, \dots, 5$. For θ_n , we are considering the following priors

$$\begin{aligned}\pi_0(\theta_1) &\sim N(0, 100) \\ \pi_0(\theta_2 | \theta_1) &\sim N(0, 100) I(\theta > \theta_1) \\ \pi_0(\theta_3 | \theta_2) &\sim N(0, 100) I(\theta > \theta_2) \\ \pi_0(\theta_4 | \theta_3) &\sim N(0, 100) I(\theta > \theta_3)\end{aligned}$$

For the variance of random effects independent vague normal priors will also be used; $\sigma_p^2 \sim \text{inverse-gamma}(0.001, 0.001)$ and $\sigma_s^2 \sim \text{inverse-gamma}(0.001, 0.001)$. The Metropolis sample algorithm as implemented in the SAS/Stat MCMC Procedure will be used to estimate the posterior distributions of the unknown parameters. Inferences will be made based on the posterior credible interval for the relevant parameters.

Hypothesis Testing

The null and alternative hypotheses for superiority are as follows:

$$\begin{aligned}H_0 \quad OR &\leq 0.67 \\ H_A \quad OR &> 0.67\end{aligned}$$

Where OR represent the cumulative odds ratio of having higher rating of the Test lens compared to the Control lens. Non-inferiority will be declared if the lower bound of the 2-sided 95% credible confidence interval is above 0.67, i.e. $P(OR=e^{\beta_1} > 0.67 | y) = 0.975$.

Primary Safety Analysis:

Lens Fit Acceptance

Lens fit acceptance will be analyzed using a Bayesian Logistic regression random-effects model to estimate the proportion of subjects' eyes wearing the Test lens having acceptable lens fitting. The regression model will include period, sequence of lens wear and first order carryover effect as fixed effects. Site and subject will be included in the model as random effects.

Let $y_{ijklm}=1$ if an acceptable lens fit is observed for eyes wearing the Test lens only and $y_{ijklm}=0$ otherwise for the m^{th} subject, from the l^{th} site, for the i^{th} eye in the j^{th} period using the k^{th} sequence.

$$y_{ijklm} \sim \text{Binary} (p_{ijklm})$$

$$p_{ijklm} = \frac{\exp(\mu_{ijklm})}{1 + \exp(\mu_{ijklm})}$$

$$\mu_{ijklm} = \beta_0 + \beta_1 \text{Lens}_{i[j,k]} + \beta_3 \text{period}_{j1} + \beta_4 \text{period}_{j2} + \beta_5 \text{sequence}_k + \beta_6 \text{Carry1}_{i[j,k]} + \gamma_1 + \delta_{m(l)} + \alpha_{j(m(l))}$$

We assume the random subject eye effects are i.i.d as $\alpha_{j(m(l))} \sim N(0, \sigma_{eye}^2)$ for eye nested within subject within clinical site, the random effect for subject are i.i.d as $\delta_{m(l)} \sim N(0, \sigma_{subject}^2)$ for subject nested within clinical site and the random clinical site effects are i.i.d as $\gamma_m \sim N(0, \sigma_{site}^2)$ for i=1, 2 (eye) , j=1, 2, 3 (period) k=1, 2 (Sequence) l=1, ...6 (Site) m=1, ...n_l(subject/site).

For the β coefficients, independent non-informative priors $N(0, 10000)$ will be used. For the variance of random effects of $\sigma_{eye}^2, \sigma_{subject}^2$ and σ_{site}^2 , independent non-informative conjugate priors inverse-gamma (0.001, 0.001) will be used. The Metropolis-Hastings algorithm as implemented in the SAS/STAT 14.2 PROC MCMC procedure will be used to estimate posterior distributions of the unknown parameters. Inferences will be made based on the posterior credible interval for the relevant parameters.

Hypothesis Testing

With respect to acceptable lens fit the null and alternative hypothesis for superiority is as follows:

$$\begin{aligned} H_0 &= p \leq 0.90 \\ H_1 &= p > 0.90 \end{aligned}$$

Where, p represents the proportion of subject eyes that achieve acceptable fit for the Test lens.

Where p is calculated as:

$$p = \frac{\exp(\mu)}{1 + \exp(\mu)}$$

$$\text{And } \mu = \beta_0 + \beta_1 + \frac{\beta_3}{3} + \frac{\beta_4}{3} + \frac{\beta_5}{2} + \frac{\beta_6}{2}$$

Success for acceptable fit will be declared if the lower bound of the 2-sided 95% credible interval of the proportion is greater than 0.90; i.e. $P(p > 0.90) \geq .975$.

If the full planned model fails to converge, reduced versions may be considered.

Primary safety analysis:

Slit Lamp Findings

Grade 3 or higher slit lamp findings will be analyzed using a Bayesian Logistic regression random-effects model to compare the Test and Control lenses. The regression model will include baseline slit lamp findings, lens type, period, sequence of lens wear and first order carryover effect. Site and subject will be included in the model as random effects.

Let $y_{ijklmn}=1$ if a Grade 3 or higher SLF is observed and $y_{ijklmn}=0$ otherwise for the n^{th} subject, from the m^{th} site, assigned to the i^{th} study lens for the j^{th} eye in the k^{th} period using the l^{th} sequence.

$$y_{ijklmn} \sim \text{Binary}(p_{ijklmn})$$

$$p_{ijklmn} = \frac{\exp(\mu_{ijklmn})}{1 + \exp(\mu_{ijklmn})}$$

$$\mu_{ijklmn} = \beta_0 + \beta_1 Lens_{ij[k,l]} + \beta_2 \text{Baseline SLF}_1 + \beta_3 period_{k1} + \beta_4 period_{k2} + \beta_5 \text{sequence}_k + \beta_6 Carry1_{i[k,l]} + \gamma_m + \delta_{n_{(m)}} + \alpha_{j_{(n(m))}}$$

We assume the random subject eye effects are i.i.d as $\alpha_{j_{(n(m))}} \sim N(0, \sigma_{eye/subject/site}^2)$ for eye nested within subject within clinical site, the random effect for subject are i.i.d as $\delta_{n_{(m)}} \sim N(0, \sigma_{subject/site}^2)$ for subject nested within clinical site and the random clinical site effects are i.i.d as $\gamma_m \sim N(0, \sigma_{site}^2)$ for $i=1,2$ (lens), $j=1, 2$ (eye) , $k=1, 2, 3$ (period) $l=1, 2$ (Sequence) $m=1, \dots, 6$ (Site) $m=1, \dots, n_m$ (subject/site).

In this model, the lens I will be determined by the period k and sequence l, therefore i is denoted as a function of j and k. We define $Lens_i=0$ for the Control lens and $Lens_i=1$ for the Test lens. The odds ratio for having a lower rate of SLFs can be written as $OR=e^{\beta_1}$.

For the β coefficients, independent non-informative priors $N(0, 10000)$ will be used. For the variance of random effects of $\sigma_{eye}^2, \sigma_{subject}^2$ and σ_{site}^2 , independent non-informative conjugate priors inverse-gamma (0.001, 0.001) will be used. The Metropolis-Hastings algorithm as implemented in the SAS/STAT 14.2 PROC MCMC procedure will be used to estimate posterior distributions of the unknown parameters. Inferences will be made based on the posterior credible interval for the relevant parameters.

Hypothesis Testing

The null and alternative hypothesis for Non-inferiority is as follows:

$$H_o: OR \geq 2$$

$$H_A: OR < 2$$

Where OR represents the cumulative odds of the Test lens having a lower rate of Grade 3 SLFs compared to the Control lens and is calculated as $OR=e^{\beta_1}$. Non-inferiority will be established if the upper limit of the 2-sided 95% credible interval is below 2, i.e. $P(OR < 2 | y)=0.975$.

If the full planned model fails to converge, reduced versions may be considered. In the event that the number of Grade 3 or higher SLFs is too small Grade 2 or higher SLFs will be analyzed and tested as described above.

